**Table 2 - Variables / Measurements**

Type of Variable	Name of Variable	Measurements
MGPT Outcomes variables	MGPT	positive (1) or negative (0)
	PV	integer number
	Likely pathogenic variables (LP)	integer number
	Name of genes with PV	descriptive
	PV in each gene	integer number
	VUS	integer number
Potential confounders variables	Age at diagnosis	Years
	Sex	Female(1)/Male(0)
	Weight	Kg
	Height	cm
	Body mass index	Kg/m 

	Presence of other diseases: Diabetes; Arterial Hypertension; Dyslipidaemia; Stroke; Heart attack);	Yes(1)/No(0) for each disease
	Stage at diagnosis (AJCC staging system);	0, I, IIa, IIb, III, IVa, IVb
	Histologic subtype;	Intestinal (1); Diffuse (2); Mixed (3)
"Exposures" variables	Personal history of other cancers	Yes (1)/No (0)
	Types of other cancer in GC patient	descriptive
	Familial history of GC	Yes (1)/No (0)
	Age of onset of each familial case of GC	integer number
	Familial history of other cancers (specifying)	descriptive
	Age of onset of each familial case of other cancers	Years
Prognostic related variables	12-months survival	Yes (1)/No(0)
	Death due to GC	Yes (1)/No(0)
	Date of death	mm/yyyy
Other variables:	Date of diagnosis	mm/yyyy
	Localization of tumor	Cardia / Fundos / Body / Antrum/pyloro
	Time since diagnosis until the current moment	months
	Surgery for GC	Yes (1)/No (0);
	Type of surgery	Total gastrectomy (1); Subtotal gastrectomy (0)
	Date of Surgery	mm/yyyy
	Histologic staging after surgery	0, I, IIa, IIb, III, IVa, IVb
	Underwent chemotherapy	Yes (1) / No (0)
	Type of chemotherapy	descriptive

	Cycles of chemotherapy	integer number
	Positive MGPT is considered when it is found at least one PV in one gene of teste	A comparative analysis will be made between the individual characteristics and tumor characteristics of positive MGPT cases with those with negative MGPT.

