## Objectives

The **main objective** of this research is to quantify and characterize the PV found in MGPT of GC patients in Alto Alentejo (Portugal).

The **specific objectives** are:

- Determine the global rate of PVs in GC patients of Alto Alentejo;
- Determine which PVs are most common in our GC population;
- Correlate the PVs found with clinical factors: Age at diagnosis; Sex; Weight; Height; Presence of other diseases (Diabetes; Arterial Hypertension; Dyslipidaemia; Stroke; Heart attack); Date of diagnosis; Stage at diagnosis; Histologic subtype; Surgery for GC; Personal history of other cancers; Familial history of GC and other cancers;
- Correlate the PVs found with prognostic factors: 12-month survival rate; mortality.

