#### **Bias**

Efforts to address potential sources of bias:

**Clear Inclusion and Exclusion Criteria:** The inclusion criteria are clear to select patients that are representative of the target population (patients with gastric adenocarcinoma) and that there is no bias in participant selection.

**Control of Confounding Factors:** There are some confounding factors that may influence the study results, such as age, sex, Weight; Height; Body mass index; **Presence of other diseases:** Diabetes; Arterial Hypertension; Dyslipidaemia; Stroke; Heart attack). This will be achieved through appropriate statistical techniques or data stratification during analysis.

**Uniformity in data records:** There was uniformity in the data recorded for each participant who agreed to be submitted to MGPT, minimizing the variability between records or the missing clinical data.

**Consistent and Accurate Data Collection:** This will be achieved through adequate training of interviewers or data collection personnel and the use of standardized data collection protocols.

**Blind Data Assessment:** After collection, the data will be pseudo-anonymized so that the researcher who analyses the data will not have access to the patient's identifying data.

**Time-Sensitive Analysis:** Data analysis takes into account the timing of data collection relative to relevant clinical events.

**Sensitivity Analysis:** It will be performed a sensitivity analyses to assess the robustness of the results across different results of MGPT and clinical factors.

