#### **Quantitative variables**

For quantitative variables we will do the descriptive statistics analyses with mean, mode, median, standard deviation, interquartile variation, maximum and minimum.

Subgroup analysis will be carried out, for each quantitative and qualitative variable, dividing patients who have positive or negative MGPT. We will analyse the effect measures of the difference between the two groups, with confidence interval (IC) 95%, and if possible, inferential statistical analysis will be conducted.

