### **Risks and Benefits**

The main benefits and expected outcomes of the study are the contribution to a better understanding of GC carcinogenesis, which could improve the diagnostic and therapeutic approach of GC patients and their relatives. In addition, this research may help to clarify whether the prevalence of hereditary GC is higher than that described in the literature (3-5%) (4,5), and may justify screening the population for this disease.

However, the use of MGPT is not without important risks, namely the identification of variants of undetermined significance (VUS), which requires careful integration of all clinical and genetic information for correct personal and family counselling. Whenever necessary, VUS carriers (as well as patients with identified PVs) will be referred to the Portuguese Institute of Oncology in Lisbon (IPOLFG) for family risk and genetic counselling. Other potential risks of this study include the psychological stress and anxiety caused by the survey and MGPT results, the need to travel to participate in the study, and the fact that the study is being conducted by non-geneticist researchers, which limits the immediate counselling that can be provided. In this way, we will have the collaboration of the psychologists of the Day Hospital, and our close collaboration with the Germano de Sousa Genetics Laboratory and the IPOLFG teams will allow an adequate response to technical questions about the MGPT. Finally, it should be noted that this observational study will only analyse the MGPT results of CG patients and will not propose any additional intervention for patients or their families.

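### A positive MGPT is defined by a PV alone, although likely pathogenic (LP) variants are counted separately, so a patient with only an LP variant is coded negative

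*Combined protocol and SAP*

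**What the plan says.** Table 2 codes MGPT as 1 (positive) or 0 (negative), with no third category. Among the MGPT outcome variables, PV, LP and VUS each have their own row and are recorded as integers. The last row of the table gives the rule for a positive test: "Positive MGPT is considered when it is found at least one PV in one gene of teste". LP does not appear in that rule.

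Genes are recorded only for PVs. There is a row for "Name of genes with PV" and a per-gene PV count, with no matching rows for LP.

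The first specific objective is to "Determine the global rate of PVs in GC patients of Alto Alentejo". The subgroup analysis (section Quantitative variables) is done by "dividing patients who have positive or negative MGPT", and Statistical methods uses the same two groups for its tests. The section Risks and Benefits adds that the study may show whether hereditary gastric cancer is more prevalent than the 3-5% given in the literature, and that this may justify population screening.

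**The concern.** One binary variable does two jobs. It separates carriers from non-carriers, and so fixes which patients count towards the carrier rate. It also forms the groups for all clinical and prognostic comparisons. Under the written rule, an LP-only patient is treated in both places like a patient with a clean test.

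With very few positives expected, moving one or two patients can decide whether the point estimate falls inside or above the 3-5% range used as the yardstick. It also changes the size of a positive group that is already too small to compare comfortably. If the meaning of PV is still open when the results are seen, the definition could be chosen with the rate in view.

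**Working it through.** **Inputs from the document.** n = 56, from 65 annual cases, 95% confidence and a 5% margin (Study size). Benchmark 3-5% (Risks and Benefits). Positive rule and separate LP row (Table 2).

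**Assumed, because the document gives neither.** The combined PV-or-LP carrier rate r: 3%, 5%, 10% and 15%. The share s of those carriers who have LP only: 10%, 25% and 50%.

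**1. The plan's own figure.** With p = 0.5 (not stated, but it reproduces the result), n0 = 1.96² × 0.25 / 0.05² = 384.15. With the finite population correction, n = 384.15 / (1 + 383.15/65) = 55.72, rounded up to 56. The stated figure reproduces and does not depend on the definition of a positive test.

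**2. Expected carriers.** 56 × 0.03 = 1.7 and 56 × 0.05 = 2.8.

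**3. Effect of one patient.** 1/56 = 1.8 percentage points. The benchmark range is only 2 points wide.

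**4. Illustrative counts with exact (Clopper-Pearson) 95% intervals.**

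| Carriers in 56 | PV only (as written) | PV or LP |
|---|---|---|
| 2 PV + 2 LP-only | 2/56 = 3.6% (0.4-12.3) | 4/56 = 7.1% (2.0-17.3) |
| 3 PV + 2 LP-only | 3/56 = 5.4% (1.1-14.9) | 5/56 = 8.9% (3.0-19.6) |

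In the first row the definition alone places the estimate inside or above 3-5%. In both rows the intervals overlap widely.

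**5. Range over the assumptions.** PV-only rate = r(1 − s). LP-only share of the coded-negative group: f = rs / (1 − r(1 − s)).

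| r | Expected carriers in 56 | PV-only rate at s = 10 / 25 / 50% | f at s = 10 / 25 / 50% |
|---|---|---|---|
| 3% | 1.7 | 2.7 / 2.25 / 1.5% | 0.3 / 0.8 / 1.5% |
| 5% | 2.8 | 4.5 / 3.75 / 2.5% | 0.5 / 1.3 / 2.6% |
| 10% | 5.6 | 9.0 / 7.5 / 5.0% | 1.1 / 2.7 / 5.3% |
| 15% | 8.4 | 13.5 / 11.25 / 7.5% | 1.7 / 4.2 / 8.1% |

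**6. Number affected at the benchmark.** From 56 × 0.03 × 0.10 = 0.2 to 56 × 0.05 × 0.50 = 1.4 LP-only patients expected.

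**7. Effect on the comparisons.** If LP carriers have the same mean as PV carriers, the expected mean difference is multiplied by 1 − f, a loss of 0.3% to 8.1% over the table. In the 3 + 2 illustration, f = 2/53 = 3.8%. The loss of positives is larger: at r = 10% and s = 50%, the expected positive group is 56 × 0.05 = 2.8 instead of 5.6.

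**The case against.** The strongest reply is that the plan is consistent on its own terms. The objectives name only PVs, the Table 2 rule counts only PVs, and a PV-only count estimates a PV-only rate without bias. This stands. A reader might infer that the planned rate is biased downward outright, but the documents support that only on condition that LP carriers belong to the target. The document also does not say whether the 3-5% benchmark itself includes LP variants.

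A second reply is that PV may be an umbrella term. LP is mentioned only in Table 2, and elsewhere the protocol speaks only of PV and VUS. Risks and Benefits provides for referral of PV and VUS carriers without mentioning LP, which would be an odd gap if LP were a class of its own. A separate row could also be a sub-count. The reading is possible, but it is nowhere stated, and an analyst building the variable from Table 2 would code LP-only patients as 0. The same clarification is needed either way.

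A third reply is that sensitivity analyses are promised, including one to "assess the robustness of the results across different results of MGPT and clinical factors". That wording, and the general list in Statistical methods (d), is too broad to commit anyone to reclassifying LP. It is true that LP is counted per patient, so the rate and the groups can be recovered later.

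Two further inferences do not hold. One is that coding LP carriers as negative pulls every group difference towards the null. Attenuation applies in expectation, only if LP carriers resemble PV carriers, and by a small amount. With one or two patients an observed difference can move either way. The other is that no new data are needed: that is true for the rate and the groups, but not for the objective on the most common variants, because genes are listed only for PVs.

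**Conclusion.** The point holds as a defect in the outcome definition. As written, LP-only patients are coded negative, and no other section corrects this. If the target is carriers of a disease-associated germline variant, the rate is understated by 1.8 percentage points per LP-only patient, and the positive group loses the same patients. That condition is implied by the comparison with hereditary prevalence, but it is not stated.

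Contamination of the negative group is a minor consequence. The actual number of LP-only patients cannot be known from the documents, so every scenario above is an illustration and not an estimate of error. The sample size calculation is unaffected. This is a cheap improvement, not a fault that invalidates the study.

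**What to change.** - In Table 2, define MGPT = 1 as at least one PV or LP variant, and MGPT = 0 as neither (VUS only or no variant).
- Reword the objectives to match, so that the rate, the most common variants and the correlations all refer to PV or LP.
- Extend the gene-name row and the per-gene count row to LP variants. The information comes from the MGPT results, which Data sources already lists for consultation.
- Prespecify the PV-only definition as a sensitivity analysis for the rate and the group tables, and fix both definitions before the results are examined.

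The cost is a few lines in the protocol, two extra fields for LP carriers and one additional analysis run. The target of 56 patients stays as it is.

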### **Ethical Issues**

This research has already been approved by the Ethics Committee and the Board of Directors of ULSAALE (Ata 06/2024, document 60 / 202400991) and it will be submitted to Ethics Committee of the Nova Medical School.

Participation in the study is voluntary, with informed consent and participants will be informed of the results before publication.

### **Risks and Benefits**

The main benefits and expected outcomes of the study are the contribution to a better understanding of GC carcinogenesis, which could improve the diagnostic and therapeutic approach of GC patients and their relatives. In addition, this research may help to clarify whether the prevalence of hereditary GC is higher than that described in the literature (3-5%) (4,5), and may justify screening the population for this disease.

However, the use of MGPT is not without important risks, namely the identification of variants of undetermined significance (VUS), which requires careful integration of all clinical and genetic information for correct personal and family counselling. Whenever necessary, VUS carriers (as well as patients with identified PVs) will be referred to the Portuguese Institute of Oncology in Lisbon (IPOLFG) for family risk and genetic counselling. Other potential risks of this study include the psychological stress and anxiety caused by the survey and MGPT results, the need to travel to participate in the study, and the fact that the study is being conducted by non-geneticist researchers, which limits the immediate counselling that can be provided. In this way, we will have the collaboration of the psychologists of the Day Hospital, and our close collaboration with the Germano de Sousa Genetics Laboratory and the IPOLFG teams will allow an adequate response to technical questions about the MGPT. Finally, it should be noted that this observational study will only analyse the MGPT results of CG patients and will not propose any additional intervention for patients or their families.

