## Introduction

**Background/ Rationale** According to data from the Global Cancer Observatory, gastric cancer (GC) ranks fifth in terms of incidence and mortality worldwide (1).

It is a multifactorial and heterogeneous disease involving both environmental and genetic factors. Although the majority of cases are sporadic, caused by environmental exposures, up to 20% of patients have a familial aggregation and of these, 3 to 5% are classified as hereditary with an identified mutation (8,9).

Three hereditary syndromes primarily affect the stomach: Hereditary Diffuse Gastric Cancer (HDGC); Gastric Adenocarcinoma and Stomach Proximal Polyposis (GAPPS); and Familial Intestinal Gastric Cancer (FIGC) (2). HDGC is an autosomal dominant syndrome, predominantly caused by germline mutations in the *CDH1* gene, which encodes the e-cadherin protein with important functions in cell aggregation, and is characterised by a high risk of early-onset diffuse GC and invasive lobular breast cancer (10). GAPPS is caused by germline mutations in *APC* promoter 1B and is characterised by the presence of fundic gland polyposis with focal dysplasia and intestinal or mixed adenocarcinoma at the level of the gastric fundus and sparing the antrum (4,11). Finally, FIGC is an autosomal dominant syndrome, still poorly characterized genetically, which is associated with an increased risk of intestinal GC (10).

Other genetic syndromes are also associated with an increased risk of GC. Some of the genes involved include *MLH1*, *MSH2*, *MSH6*, and *PMS2* (Lynch Syndrome - LS), *TP53* (Li-Fraumeni Syndrome), *APC* (PAF and ADC / proximal polyposis of the stomach) and *MUTYH* (Polyposis Associated MUTYH), *BMPR1A* and *SMAD4* (Juvenile Polyposis Syndrome), *STK11* (Peutz-Jegher Syndrome) and *PTEN* (Cowden Syndrome) (3–5).

As GC is a neoplasm with numerous somatic and hereditary mutations involved in its carcinogenesis, the use of MGPT can be crucial, as it performs the analysis of hereditary mutations in a significant number of genes simultaneously (depending on the genes included in the panel) (6,7). In addition to the described mutations, MGPT has allowed the identification of new genetic mutations associated with GC risk, including in the *BRCA 1/2*, *PALB2*, *ATM* and *RAD51C* genes (typically associated with hereditary breast and ovarian cancer), *MAP3K6*,

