MYD88, among others (9,12–17). However, the use of MGPT, especially in unselected GC patients, is not without risks, such as the unexpected detection of PV in genes not strictly associated with the phenotype (secondary findings) or, more commonly, the high rate of variants of unknown significance (VUS), which can raise important questions regarding the uncertainty of how to approach these patients (18). Therefore, some studies advocate that MGPT or single gene testing (SGT) should be offered only to selected patients, especially those with suspected HDCG (5,19–21). On the other hand, the evidence of many other germline mutations associated with GC and the lack of genetic characterisation of FIGC justifies the growing interest in performing MGPT in unselected patients with GC (10,18,22,23). Although these studies suggest a benefit in the use of MGPT in unselected patients with GC, this test is not yet widely used.

In Portugal, the incidence and mortality rates of GC have been increasing over the last few decades. It is therefore important to better understand the genetic characteristics of GC in this country in order to develop better strategies for managing this disease.

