### Setting

This study takes place at the Unidade Local de Saúde do Alto Alentejo (ULSAALE). The MGPT was always performed in the same laboratory (Germano de Sousa – Centro de Genética Laboratorial) using peripheral blood samples from patients with GC.

Two types of MGPT were used:

- MGPT 4005 (15 genes): APC, ATM, BLM, BMPR1A, CDH1, CTNNA1, EPCAM, MLH1, MSH2, MSH6, PMS2, PTEN, SMAD4, STK11/TP53.
- MGPT 4013 (30 genes): ATM, BARD1, BLM, BRCA1, BRCA2, BRIP1, CDH1, CHEK2, EPCAM, FANCC, MLH1, MRE11A, MSH2, MSH6, MUTYH,

NBN, NF1, PALB2, PMS2, PTEN, RAD50, RAD51C, RAD51D, RECQL4, RINT1, SLX4, SMARCA4, STK11, TP53, XRCC2.

The majority of patients with GC were tested with MGPT 4005. Patients with neoplasms other than GC or with a family history of other neoplasms were tested with MGPT 4013. The decision to perform MGPT and the choice of panel type were made in multidisciplinary consultation.

The recruitment process takes place between January 2023 and December 2024. All data will be collected and entered in a database until September 2025

The manuscript for publication will be written between October and November 2025.

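### The only planned prevalence figure counts a PV in any tested gene, so it cannot by itself show whether hereditary GC exceeds 3-5%

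*Combined protocol and SAP*

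**What the plan says.** - **Intended reading.** Risks and Benefits expects that the research "may help to clarify whether the prevalence of hereditary GC is higher than that described in the literature (3-5" per cent), and adds that the result might support screening of the population.
- **Estimand.** The first specific objective is to "Determine the global rate of PVs in GC patients of Alto Alentejo". No other prevalence figure is planned.
- **Positivity.** Table 2: "Positive MGPT is considered when it is found at least one PV in one gene of teste". There is no restriction by gene. Table 2 also records the names of the genes with a PV and the number of PVs in each.
- **Panels.** Setting lists "MGPT 4005 (15 genes") and "MGPT 4013 (30 genes"). Most patients had the first. Patients with another neoplasm, or a family history of one, had the second.
- **Genes tied to GC.** The Introduction covers the primary gastric syndromes and then says "Other genetic syndromes are also associated with an increased risk of GC". Between them these paragraphs name 12 genes. It then names newer GC-associated genes, of which BRCA1, BRCA2, PALB2, ATM and RAD51C are on a panel.
- **Acknowledged risk.** The Introduction warns of "the unexpected detection of PV in genes not strictly associated with the phenotype (secondary findings"), but no rule for counting them follows.
- **Benchmark.** The Introduction first mentions the up to 20% of patients with familial aggregation and then says that "of these, 3 to 5% are classified as hereditary with an identified mutation". Risks and Benefits uses the same 3-5% as a prevalence.

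**The concern.** The figure the study will produce and the figure it is meant to inform are different quantities. One is the share of tested patients with a PV in any panel gene. The other is the share with hereditary GC, which the protocol never defines by gene. A PV in a gene unrelated to the stomach raises the first and leaves the second unchanged. The panel that holds nearly all the genes not tied to GC goes to patients selected for other cancers in themselves or their families, so such findings are plausible.

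What is at stake is one of the study's stated main benefits. A reader who sees a pooled rate above 5% may conclude that hereditary GC is more common in Alto Alentejo than published, and may carry that conclusion into the screening remark. Every participant has gastric adenocarcinoma (Participants). The study therefore gives neither a carrier frequency in the general population nor a GC risk among carriers.

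**Working it through.** **1. The plan's own figure.** Study size gives 56 patients from 65 annual cases, 95% confidence and a 5% margin. With an expected proportion of 0.5 (assumed, as none is stated):

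- n0 = 1.96² × 0.25 / 0.05² = 384.1
- n = 384.1 / (1 + 383.1/65) = 55.7, rounded up to 56

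The figure reproduces and is used below as the denominator.

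**2. Gene counts from the Setting lists.**

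- Distinct genes: 15 + 30 − 11 shared = 34. Each patient has one panel, so no one need be tested for all 34.
- Syndrome genes in the Introduction (12): CDH1, APC, MLH1, MSH2, MSH6, PMS2, TP53, MUTYH, BMPR1A, SMAD4, STK11, PTEN.

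| | MGPT 4005 | MGPT 4013 |
|---|---|---|
| Genes | 15 | 30 |
| Syndrome genes | 11 (no MUTYH) | 9 (no APC, BMPR1A, SMAD4) |
| Named newer genes | 1 (ATM) | 5 |
| Not tied to GC in the body text | 3 (BLM, EPCAM, CTNNA1) | 16 |

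The 16 are BARD1, BLM, BRIP1, CHEK2, EPCAM, FANCC, MRE11A, NBN, NF1, RAD50, RAD51D, RECQL4, RINT1, SLX4, SMARCA4 and XRCC2. CTNNA1 is linked to hereditary diffuse GC by the title of a cited reference; crediting it leaves 2 untied genes on MGPT 4005. Syndrome genes on both panels: 11 + 9 − 12 = 8 (CDH1, MLH1, MSH2, MSH6, PMS2, PTEN, STK11, TP53).

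**3. Effect of one finding at n = 56.** Each extra positive patient adds 1/56 = 1.8 points. Exact (Clopper-Pearson) 95% intervals:

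- 2/56 = 3.6% (0.4-12.3%)
- 3/56 = 5.4% (1.1-14.9%)
- 7/56 = 12.5% (5.2-24.1%), the smallest count whose lower limit is above 5%

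**4. Illustration under assumptions.** The documents give neither the panel split nor a rate of unrelated PVs. Let h be the true rate in GC genes, f the share on MGPT 4013 and s the share of those with a PV in an untied gene, independent of h. Ignoring genes missed by either panel, the any-gene rate is 1 − (1 − h)(1 − f·s). The last column is the binomial chance of 3 or more positives in 56, that is, an observed rate above 5%.

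| h | f | s | Any-gene rate | Chance of observing >5% |
|---|---|---|---|---|
| 3% | any | 0% | 3.0% | 24% |
| 3% | 20% | 2% | 3.4% | 30% |
| 3% | 40% | 5% | 4.9% | 53% |
| 3% | 40% | 10% | 6.9% | 75% |
| 5% | any | 0% | 5.0% | 54% |
| 5% | 40% | 10% | 8.8% | 88% |

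The rows with s = 0 show that an observed rate above 5% is weak evidence even without unrelated PVs.

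**5. Benchmark denominator.** Read literally, the Introduction's wording gives at most 0.20 × 3% = 0.6% to 0.20 × 5% = 1.0% of all GC. Risks and Benefits implies 3-5%. The two differ by a factor of five.

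**The case against.** The sentence in Risks and Benefits is a hedged statement of expected benefit. Objectives, Quantitative variables and Statistical methods plan no comparison with 3-5%, and nowhere is a positive test equated with hereditary GC. A reader might infer a planned formal test against the benchmark; the documents do not support that. Objectives also commits to reporting which PVs are most common, so the genes behind the rate should be visible. These points stand and limit the concern to interpretation. They do not remove it, because no gene-restricted rate is planned, and choosing the genes after the results are seen would be post hoc.

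A reader might also treat every PV outside the 12 syndrome genes as a secondary finding. That goes too far. The Introduction presents both gene lists as incomplete, calls five further panel genes GC-associated, and cites a source for CTNNA1. The 16 is a count of what the text leaves untied, not a biological judgement. For the same reason the 21 of 30 genes on MGPT 4013 outside the syndrome list should not be read as unrelated to GC.

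There is a partial offset. MGPT 4013 omits APC, BMPR1A, SMAD4 and CTNNA1, and MGPT 4005 omits MUTYH, so some GC-linked PVs can be missed. Finally, the genes behind the published 3-5% cannot be seen from the documents. That is a further reason to define both sides of the comparison.

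**Conclusion.** The concern holds as a mismatch between the planned rate and the question it is offered to inform. At 56 patients, one PV in an unrelated gene is enough to move the observed rate from inside 3-5% to above it. It does not follow that the pooled rate will be inflated, or by how much. The size depends on the panel split and the frequency of unrelated PVs, neither of which is given, and the omitted genes act in the other direction. Nor would a move from 3.6% to 5.4% be statistically distinguishable, since both exact intervals contain the whole of 3-5%. The conclusion rests on the planned 56 patients and on the gene lists as printed. It should be corrected before analysis, but it does not threaten the descriptive aim of counting and listing PVs.

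**What to change.** Prespecify two rates, each with an exact 95% interval:

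- **(a) Any-gene PV rate**, shown by panel.
- **(b) PV rate in a fixed list of GC-predisposition genes.** Start from the 12 syndrome genes in the Introduction. Explicitly assign CTNNA1, BRCA1, BRCA2, PALB2, ATM and RAD51C, and show them as a separate tier.

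Set only (b) beside the literature value, and list the remaining PVs as secondary findings. Use the 8 syndrome genes common to both panels for a sensitivity rate only. As the main rate it would drop APC, BMPR1A and SMAD4, which the majority panel tests, as well as MUTYH.

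Reconcile the benchmark's denominator between the Introduction and Risks and Benefits, and say which one the comparison uses. Limit the screening statement to germline testing of GC patients, the only group studied.

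The cost is some SAP wording and one extra rate from gene names already recorded in Table 2. The downsides are a smaller numerator, a less favourable headline figure and some judgement in fixing the gene list.
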